20. APPENDIX I. CARDIAC SAFETY MONITORING (ECG)

1. Requirements for Testing

ECG equipment and supplies will be provided by the centralized cardiac safety vendor and should be used for all in-clinic protocol ECG assessments.

- All 12-lead ECGs will be recorded in the same manner.
- The study center personnel must be adequately trained in performing ECGs on the specific ECG equipment used in this protocol that is provided by the cardiac safety vendor.
- To the extent possible, the same ECG machine and personnel should be used to acquire a subject's ECGs throughout the period of their participation in the study.
- ECGs will be recorded with at least one 10-second single-lead tracing recorded from Lead II.

2. Subject Restrictions and Instructions

- Prior to ECG acquisition, the subject will have rested at least 5 minutes in the supine position and will remain so until the ECG is obtained.

3. Reporting

- It is the responsibility of the Investigator to perform a safety review of the ECG data for changes from previous assessments and/or emergent cardiac dysfunction, and to determine subjects' eligibility or continuance in the study.
- ECGs will be reviewed, signed and dated by the Investigator listed on the Form FDA 1572 (MD or DO) after each ECG collection. The same Investigator should review all ECG reports for a given subject whenever possible.
- For all ECGs, a report will be provided by the cardiac safety vendor to the study center for review and signature.
- The ECG tracing will be kept with subject's source documentation and / or CRF unless it is specified otherwise. The original ECG and the cardiologist's overread will be retained at the study center.

4. Data Standardization

ECG data will be transmitted to a centralized cardiac safety vendor and centrally over-read and interpreted using standardized procedures.

21. APPENDIX II: GUIDELINE FOR PRE-SWITCH ANTIPSYCHOTIC TAPER

- Prior to the first dose of investigational product (IP), plan a taper strategy of the pre-switch antipsychotic for each subject (changes to the plan may be needed during the study based on subject response / tolerability)
 - Consider treatment history, clinical presentation and reason for switch
 - Attempt to reduce the pre-switch antipsychotic by at least 50% half-way through the taper
- If the pre-switch antipsychotic is considered to have a strong binding affinity for muscarinic-cholinergic (M1) and/or histaminergic (H1) receptors, consider a longer, more gradual taper (ie, 4 - 6 weeks to complete)
 - Examples: asenapine, olanzapine, quetiapine
- If the pre-switch antipsychotic is considered to have a strong binding affinity for dopaminergic (D2, D3) receptors, consider a moderately gradual taper (ie, 3 - 5 weeks to complete)
 - Examples: lurasidone, paliperidone, risperidone, ziprasidone, haloperidol (and other first-generation antipsychotics)
- If the pre-switch antipsychotic is considered to have a long half-life, a faster, less gradual taper may be appropriate (ie, 2 - 3 weeks to complete)
 - Examples: aripiprazole, brexpiprazole, cariprazine
- For any type of pre-switch antipsychotic, if the dose is at the upper end of the recommended daily dose range for that particular medication, consider a longer, more gradual taper
- If the subject has been taking a D2 antagonist for lengthy period of time, consider longer more gradual taper

22. APPENDIX III. HALOPERIDOL EQUIVALENT DOSES

Medications	Haloperidol Equivalent (12 mg)
Typical Antipsychotics	
Chlorpromazine	600 mg
Chlorprothixene	500 mg
Fluphenazine	15 mg
Haloperidol	12 mg
Perphenazine	40 mg
Thioridazine	500 mg
Thiothixene	30 mg
Trifluoperazine	25 mg

Medications	Haloperidol Equivalent (12 mg) in mg
Atypical Antipsychotics	
Amisulpride	800
Aripiprazole	30
Asenapine	30
Brexpiprazole	4.5
Cariprazine	4.5
Clozapine	900
Haloperidol	12
Iloperidone	24
Lurasidone	120
Olanzapine	20
Paliperidone	9
Quetiapine	700
Risperidone	6
Sertindole	36
Sulpiride	800
Ziprasidone	160

For antipsychotics not listed in the tables above, please consult the Medical Monitor.

References:

https://www.whocc.no/atc_ddd_index/?code=N05AX15 [assessed 02 Sept 2020]

Stahl SM. A pocket guide to atypical antipsychotics: dosing, switching, and other practical information. Arbor Scientia; 2013.

23. APPENDIX IV. CLINICAL LABORATORY TESTS

Detailed instructions will be provided in a study center manual.

The following clinical laboratory tests are to be performed.

Clinical Safety Panel

HEMATOLOGY: (Differential reported as % and absolute value)

Hemoglobin, Hematocrit, Platelet Count, Red blood cell (RBC) Count, White blood cell (WBC) - Total Count, WBC Differential, (Basophils, Eosinophils, Lymphocytes, Monocytes, Neutrophils)

BLOOD CHEMISTRIES: Alanine aminotransferase (ALT), Albumin, Alkaline Phosphatase (ALP), Aspartate aminotransferase (AST), Bicarbonate, Bilirubin (Total, Direct, Indirect), Blood Urea Nitrogen (BUN), Calcium (Ca), Chloride (Cl), Cholesterol, Creatinine, Creatinine clearance (calculated GFR), Creatinine phosphokinase (CPK), Free T3, Free T4, HDL-Cholesterol, hs C-reactive Protein (CRP), Glucose, Hemoglobin A1c (HbA1c), LDL-Cholesterol, Magnesium (Mg), Phosphorus (P), Potassium (K), Prolactin, Protein (Total), Serum Insulin, Sodium (Na), Thyroid stimulating hormone (TSH), Triglycerides, Uric Acid

URINALYSIS: Blood, Glucose, Ketones, Leukocyte esterase, Microscopic examination, Nitrites, pH, Protein

URINE DRUG SCREENING / RAPID URINE DRUG SCREENING: Amphetamines, Barbiturates, Benzodiazepines, Cannabinoids (Urine Drug Screen), Cocaine, Marijuana (THC) (Rapid Urine Drug Screen), Methamphetamines, Methadone, Methylenedioxymethamphetamine (MDMA), Phencyclidine (PCP), Opiates, Oxycodone

SEROLOGY PANEL: Hepatitis B Ag, Hepatitis C Ab

OTHER TESTS: Serum Pregnancy (β -hCG) (in female subjects only), Urine Pregnancy Test (in female subjects only), Rapid Urine Pregnancy Test (in female subjects only), Follicle stimulating hormone (in female subjects with suspected menopause)

Laboratory reports will be initialed and dated on all pages by the Investigator listed on the Form FDA 1572 (MD or DO). Laboratory test results will be reviewed by the Investigator as they become available. The Investigator must determine the clinical significance of all out-of-range lab values (except drug screens). Possibly drug-related or clinically relevant abnormal values of uncertain causality must be repeated. Any abnormal values that persist should be followed until the test(s) has (have) normalised or stabilised.

24. APPENDIX V. PHARMACOKINETIC SAMPLING AND SAMPLE HANDLING GUIDELINE

Please refer to the Laboratory Investigator Manual for all collection and shipping instructions.

BLOOD SAMPLES FOR PLASMA PHARMACOKINETICS

When blood sample for PK assessment and clinical lab sample collections share the same designated time points (including predose sample), the blood samples should be collected during the same venipuncture as long as possible.

For each defined PK sampling time point, collect 6 mL blood sample into a K₂EDTA treated tube. Invert gently 8 to 10 times. Keep the blood collection tube on wet ice upon blood draw, and centrifuge for 20 minutes at ca. x 1300 g to isolate plasma within 30 minutes of blood draw. To ensure a more homogenous sample, all plasma samples should first be transferred to 1 tube, capped and mixed well. Split the harvest plasma sample into 2 polypropylene tubes with approximately equal volume, and label as Primary and Backup. Freeze plasma tubes in a freezer set at approximately -20°C or lower. The date and clock time of blood collection must be recorded.

Blood must be collected from all subjects at the time points indicated below.

All samples will be shipped with sufficient dry ice protection.

Study Day	Collection Time	Volume Collected
Day 1	Pre-dose	6 mL
Day 8	Anytime (Actual date and clock time will be recorded)	6 mL
Day 29	Anytime (Actual date and clock time will be recorded)	6 mL
Day 57 / EOT / ET	Anytime (Actual date and clock time will be recorded)	6 mL

1. INTRODUCTION

This document describes the rules and conventions to be used in the presentation and analysis of safety, effectiveness and pharmacokinetic (PK) data for Protocol SEP361-308. It describes the data to be summarized and analyzed, including specifics of the statistical analyses to be performed.

This statistical analysis plan (SAP) is based on protocol version 5.00, dated 06NOV2023.

A Pre-Lock Data Review (PLDR) and Important Protocol Deviation (IPD) Review Plan will be written to describe the process and the outputs to be delivered during the IPD/BDR meetings.

The scope of this SAP does not include calculation and statistical analysis of PK parameters of SEP-363856; individual SEP-363856 PK parameters will be determined using population PK approach and results will not be reported in the clinical study report (CSR).

2. STUDY OBJECTIVES AND ENDPOINTS

2.1. STUDY OBJECTIVES

2.1.1. PRIMARY OBJECTIVE

The primary objective is to evaluate the safety and effectiveness of switching clinically stable outpatients with schizophrenia from a typical or atypical antipsychotic to SEP-363856 over a period of 8 weeks as assessed by the percentage of subjects who discontinue from the study due to an adverse event or lack of efficacy

2.1.2. SECONDARY OBJECTIVE

The secondary objective is to evaluate the safety and effectiveness of switching clinically stable outpatients with schizophrenia from a typical or atypical antipsychotic to SEP-363856 over a period of 8 weeks as assessed by the percentage of subjects who discontinue for any reason (ie, all causes of discontinuation)

Document: PPD

Author: PPD

Version Number:

1.0

Version Date:

06MAY2024

2.1.3. OTHER OBJECTIVES

- To evaluate the tolerability and safety of switching clinically stable outpatients with schizophrenia from a typical or atypical antipsychotic to SEP-363856 over a period of 8 weeks using:
 - Adverse event reports
 - Clinical laboratory tests
 - Vital sign measurements
 - 12-lead electrocardiograms (ECG)
 - Columbia – Suicide Severity Rating Scale (C-SSRS)
 - Barnes Akathisia Rating Scale (BARS)
 - Abnormal Involuntary Movement Scale (AIMS)
 - Simpson-Angus Scale (SAS)
- To evaluate the effectiveness of SEP-363856 using:
 - Positive and Negative Syndrome Scale (PANSS)
 - Clinical Global Impression-Severity (CGI-S) scale
 - Clinical Global Impression-Improvement (CGI-I) scale
 - Brief Negative Symptom Scale (BNSS)
- To evaluate the effects of SEP-363856 on health-related quality of life as measured by the Short Form Health Survey (SF-12)
- To evaluate the effects of SEP-363856 on functional capacity as measured by the Personal and Social Performance Scale (PSP)
- To evaluate medication satisfaction as measured by the Medication Satisfaction Questionnaire (MSQ)
- To evaluate sleep as measured by the Pittsburgh Sleep Quality Index (PSQI)
- To evaluate the impact of SEP-363856 on healthcare resource utilization (HCRU)

Document:

PPD

Author:

PPD

Version Number:

1.0

Version Date:

06MAY2024

2.2. STUDY ENDPOINTS

2.2.1. PRIMARY ENDPOINT

- Percentage of subjects who discontinue for clinical reasons (ie, discontinued due to an adverse event [AE] or lack of efficacy)

2.2.2. SECONDARY ENDPOINT

- Percentage of subjects who discontinue for any reason (ie, all causes for discontinuation)

2.2.3. OTHER ENDPOINTS

- The incidence of overall AEs, serious adverse events [SAE]s, and AEs leading to discontinuation
- Observed values and changes from Baseline in clinical laboratory tests (hematology, chemistry and urinalysis)
- Observed values and changes from Baseline in vital signs (including body weight, body mass index [BMI], waist circumference, temperature, blood pressure [supine and standing], heart rate [supine and standing] and respiratory rate)
- Observed values and changes from Baseline in 12-lead ECG parameters
- Frequency of subjects with suicidal ideation and suicidal behavior based on the C-SSRS
- Changes from Baseline in BARS, AIMS and SAS scores
- Changes from Baseline to Week 8 in:
 - PANSS total score and subscale scores (positive, negative, and general psychopathology)
 - PANSS Marder Factor (five-factor) scores (positive, disorganized, negative, hostility, and depression/anxiety), and Uncorrelated PANSS Score Matrix (UPSM)

Document: PPD

Author: PPD

Version Number:

1.0

Version Date:

06MAY2024

- o CGI-S score
- o BNSS total score
- o SF-12 scores
- o PSP total score
- o MSQ score
- o PSQI global score
- CGI-I score at Week 8
- HCRU (including numbers of physician office visits, emergency room [ER] visits and hospitalizations, length of hospital stays, employment status and average number of hours caregiver(s) spends helping subjects per week.)
- Nicotine use at baseline and Week 8 (end of treatment [EOT]/early termination [ET])

3. STUDY DESIGN

3.1. GENERAL DESCRIPTION

This is an 8-week, outpatient, multicenter, open-label, single-group, flexible-dose study designed to evaluate the safety and tolerability, as well as effectiveness of switching clinically stable adult subjects with schizophrenia from a typical or atypical antipsychotic to SEP-363856. This study is projected to enroll approximately 120 subjects into a single treatment group (SEP-363856). Over the 8-week treatment period, subjects will receive flexibly dosed SEP-363856 (50 to 100 mg/day) and the investigator will have the discretion to discontinue each subject's pre-switch antipsychotic treatment by the end of Week 2, 3, 4, 5, or 6.

Once the pre-switch antipsychotic has been fully discontinued, subjects will continue to receive SEP-363856 flexible 50 to 100 mg/day until study endpoint, at the end of Week 8. Study medication will be taken at the same time each evening at bedtime and can be taken with or without food.

The study will consist of three periods: Screening/Washout (up to 21 days), Treatment (8 weeks) and a Follow-up visit (7 ± 2 days after the last dose of study medication for those subjects who discontinue prior to the Week 8 visit or who complete the study but do not enroll in the open-label extension study SEP361-309). If necessary, subjects may return to the clinic at any time for an unscheduled visit.

A study schematic is presented in Figure 1.

Document:

PPD

Author:

[figure not shown]
PPD

Version Number:

1.0

Version Date:

06MAY2024

Figure 1: Study schematic

3.2. METHOD OF ASSIGNING SUBJECTS TO TREATMENT GROUPS

This is an open label study. There is no randomization planned in this study. All subjects will receive flexible dosing with SEP-363856 (50 to 100 mg/day).

3.3. BLINDING

This is an open-label study. All subjects will receive flexible dosing with SEP-363856 (50 to 100 mg/day).

3.4. DETERMINATION OF SAMPLE SIZE

Document:	PPD	
Author:	PPD	Version Number: 1.0 Version Date: 06MAY2024

The sample size was determined by the width of the 95% confidence interval for the proportion of subjects who may discontinue due to clinical reasons by Week 8 to ensure the precision of the estimate of the true discontinuation rate due to clinical reasons. Assuming, 1) 15% of SEP-363856 treated subjects will experience discontinuation due to clinical reasons by Week 8, and 2) 6.4% as the half width (the distance between the upper/lower limits to the point estimate) of the 95% confidence interval (ie, [8.6%, 21.4%]), approximately 120 subjects was planned for enrollment. Due to higher than predicted rates for enrollment, retention, and completers in study 308, the SMPA team decided to revisit the assumption of 15% SEP-363856 treated subjects discontinuation rate due to clinical reasons by Week 8. Using the proportion from the data at time of revisiting, the discontinuation rate due to clinical reasons by Week 8 was approximately 7.2%. With 7.2% as the assumption, 100 subjects would provide a half width of 5.1% half width and was deemed to be sufficient. 101 subjects were enrolled.

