6.6. STATISTICAL TESTS

The default significance level will be 5%; confidence intervals (CIs) will be 95%. All CIs will be two-sided, unless otherwise specified in the description of the analyses or the outputs.

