16. EFFECTIVENESS OUTCOMES

Unless otherwise specified, the effectiveness analysis and summary tables will include the columns: SEP-363856 50 to 100 mg/day.

All analyses of the effectiveness variables will be based on the EFF population and, for selected variables/analyses, the PP population by the actual treatment group.

Descriptive statistics presented for effectiveness outcomes include sample size, mean, standard deviation, minimum, median, maximum, and a 95% confidence interval. Confidence intervals will be based on means and standard deviations estimated without adjustment for any center or baseline effects.

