17.1. DISCONTINUATION DUE TO CLINICAL REASONS

Discontinuation for clinical reasons is defined as reasons due to AE or lack of efficacy. AE will follow the definition as in section [17.3](#).

The percentage of subjects who discontinued for clinical reasons will be calculated by a proportion consisting of the number of subjects who experience a discontinuation event due to clinical reasons as the numerator divided by the number of subjects in the safety population as the denominator multiplied by 100 along with a corresponding 95% confidence interval (CI).

The number and percentage of subjects, who discontinued early from the open-label treatment period (including both clinical reasons, ie, discontinued due to an AE or lack of efficacy (primary endpoint) and any reason for discontinuation (secondary endpoint)) will be presented.

The time-to-discontinuation for clinical reasons will be summarized descriptively, (eg, n, median, 25th percentile, 75th percentile, minimum and maximum, and 95% CI on median, where possible).

Time to discontinuation for clinical reasons since first dose of study medication will be plotted using Kaplan-Meier curves for the safety population by treatment group. Probability of remaining on treatment at Day 56, median time to discontinuation, and their 95% confidence intervals will be estimated using the Kaplan-Meier method for the safety population by treatment group.

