17.2. DISCONTINUATION DUE TO ANY REASONS

The percentage of subjects who discontinued for any reason (ie, all cause discontinuation). The percentage will be calculated similarly as that of the primary endpoint along with a corresponding 95% CI.

Kaplan-Meier analysis as in section [17.1](#) will be performed for time to discontinuation for any reasons.

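### Must the SAP name a confidence interval method for the discontinuation proportions, given that its planning text shows only a symmetric half width of 5.1%?

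*SAP*

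**What the plan says.** SAP 3.4 starts from the assumption that "15% of SEP-363856 treated subjects will experience discontinuation due to clinical reasons by Week 8". It takes a half width of 6.4%, defined as the distance from either limit to the estimate, with limits of 8.6% and 21.4%, and on that basis "approximately 120 subjects was planned for enrollment". After the clinical discontinuation rate in the accruing data was seen to be about 7.2%, the section adds "With 7.2% as the assumption, 100 subjects would provide a half width of 5.1% half width" and reports that 101 subjects were enrolled.

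For the analysis, SAP 17.1 divides the number of clinical discontinuations by the safety population and asks only for a corresponding 95% interval. SAP 17.2 follows suit: "The percentage will be calculated similarly as that of the primary endpoint along with a corresponding 95% CI". Protocol 15.3.5.1 says no more. The general rule in SAP 6.6 fixes the level at 95% and adds "All CIs will be two-sided, unless otherwise specified in the description of the analyses or the outputs". The one explicit basis for an interval, "Confidence intervals will be based on means and standard deviations estimated without adjustment for any center or baseline effects", stands in SAP 16 and concerns effectiveness scores, not these proportions. SAP 17.1 also requires a Kaplan-Meier probability of remaining on treatment at Day 56 with a 95% interval, and 17.2 repeats that analysis for all-cause discontinuation.

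**The concern.** The primary result of this single-arm study is one percentage with its interval, and protocol section 15 leaves the statistical detail to the SAP. The SAP repeats the protocol's wording without a method. The only binomial interval shown anywhere is the planning one, which has equal arms. With an expected rate of 7.2% and about 100 subjects there are only around seven events, and a symmetric interval fits poorly. Its upper limit, which tells the reader how high discontinuation might be, falls short of the Wilson and exact limits.

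Two things would be at stake. If the planning form were carried over, the reported upper limit would be too low, and most misses would understate discontinuation. If the choice stayed open, it could be made with the event count in view, since the study is open-label and the rate has already been looked at once.

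**Working it through.** **Inputs.** From SAP 3.4: 15% with 120 subjects, half width 6.4%, limits 8.6% and 21.4%; 7.2% with 100 subjects, half width 5.1%; 101 enrolled. From SAP 6.6: 95%, two-sided, so z = 1.96. The final event count is not in the documents, so the counts below are illustrations. They assume that all 101 enrolled subjects are in the safety population.

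**1. Reproduce the plan's figures.** Wald half width = z·√(p(1−p)/n).

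- 15%, n = 120: 1.96·√(0.15×0.85/120) = 6.39 points, giving 8.61% to 21.39%. This matches the stated 6.4% and both limits. Wilson would give 9.7% to 22.5% and Clopper-Pearson 9.1% to 22.7%, so the planning form is Wald.
- 7.2%, n = 100: 1.96·√(0.072×0.928/100) = 5.07 points, which rounds to the stated 5.1%.

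Both figures are arithmetically correct.

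**2. Compare methods at 7.2% with n = 100.** Here 7.2 events is treated as a continuous value. The Wilson centre is (p + z²/2n)/(1 + z²/n) = (0.072 + 0.0192)/1.0384 = 0.0878. Its half width is z·√(p(1−p)/n + z²/4n²)/(1 + z²/n) = 0.0522. Clopper-Pearson takes the 2.5% point of Beta(7.2, 93.8) and the 97.5% point of Beta(8.2, 92.8).

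| Method | Lower % | Upper % | Arm below | Arm above | Average half width |
|---|---|---|---|---|---|
| Wald | 2.13 | 12.27 | 5.07 | 5.07 | 5.07 |
| Wilson | 3.57 | 14.00 | 3.63 | 6.80 | 5.22 |
| Clopper-Pearson | 2.99 | 14.15 | 4.21 | 6.95 | 5.58 |

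The Wald upper arm is short by 6.80 − 5.07 = 1.73 points (Wilson) or 6.95 − 5.07 = 1.88 (exact). Its lower arm is long by 5.07 − 3.63 = 1.44 or 5.07 − 4.21 = 0.86. The interval is mainly shifted down. Average half width differs by only 0.15 points from Wilson and 0.51 from exact.

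**3. Whole-number counts out of 101.**

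- 7 events: Wald 2.0–11.9%, Wilson 3.4–13.6%, exact 2.8–13.8%.
- 8 events: Wald 2.7–13.2%, Wilson 4.1–14.9%, exact 3.5–15.0%.
- Upper limits (Wald, Wilson, exact) are 7.8, 9.7 and 9.8% at 4 events, and 15.7, 17.3 and 17.5% at 10. On unrounded limits, Wald is lower by 1.5 to 2.1 points across that range.

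**4. Coverage at n = 101 and a true rate of 7.2%**, by summing binomial probabilities.

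| Method | Coverage % | True rate above the upper limit % (nominal 2.5) |
|---|---|---|
| Wald | 93.2 | 6.2 |
| Wilson | 95.0 | 2.1 |
| Clopper-Pearson | 96.6 | 2.1 |

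Averaged over true rates of 6% to 9%, coverage is 92.3% for Wald (range 87.5 to 94.7), 95.2% for Wilson and 96.9% for exact. At n = 120 Wald averages 92.8% over the same rates, so cutting the sample did not create the weakness.

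**5. What depends on the limit.** Protocol 7.3.4 calls the primary outcome a descriptive measure. SAP 7.1 and 7.4 state that no statistical comparison is made. Neither document sets a reference rate or a success threshold. SAP 17.1 reports numbers as well as percentages, so any reader can recompute the interval by any method.

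**The case for a change.** The strongest case for a change is that this is the primary endpoint, that the gap costs one line to close, and that 1.7 to 1.9 points is over a third of the stated 5.1-point precision. The team had also seen the accruing rate before this SAP version, so an unnamed method can be chosen with knowledge of the data.

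Part of this stands. The method is unnamed, and Wald would be a poor choice here. The rest carries less weight.

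- The planning formula is not an instruction for the analysis, and the SAP nowhere says Wald will be used.
- SAP 8 says that templates supplied with the SAP set the content of the tables, and 6.6 lets the outputs specify interval details. Those templates are not in these documents and may name the method.
- Naming a method in the current SAP would still come after the 7.2% had been seen, so it would restore little blindness.
- The interval is not the only statement of uncertainty. The Day 56 Kaplan-Meier probability carries its own 95% interval. Its variance method is also unstated, so the primary proportion has not been singled out for less detail.
- For the secondary endpoint no rate is assumed. It cannot be below the primary rate, and the gap narrows as the rate rises: the Wald and Wilson upper limits differ by about 1.0 point at 20/101.

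**Conclusion.** No change to the plan is needed. The 5.1% in SAP 3.4 is right for the normal approximation. As a measure of overall precision it lies within 0.15 points of Wilson and 0.51 of Clopper-Pearson. Enrolment is complete, so restating it with two arms would alter no result.

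The missing method name in 17.1 and 17.2 is a gap in detail for a descriptive interval, of the kind that analysts or table templates routinely fill. Even the poorest of the three choices moves the upper limit by 1.5 to 2.1 points for 4 to 10 events in 101, and no stated conclusion turns on a shift of that size. At a true rate of 7.2% it would lower coverage to 93.2%.

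This rests on a final clinical discontinuation count near the 7.2% seen during the study, on all 101 enrolled subjects being in the safety population, and on the result being read as the documents present it, without a threshold. If a limit were later held against a fixed rate, the choice of method would matter more.
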